Control group and treatment effects estimated separately. The inclusion of two test dose levels (Test 1 & 2) allows minor adjustment, for example by interpolation, between test dose levels to identify the fraction size most closely resembling the control schedule in terms of late change in breast/chest wall appearance and other adverse effects. The primary comparison is the rate of local tumour control at this 5-fraction dose level compared to the 15-fraction control. Since local relapse rates are so low, and no measurable difference in local relapse between the two test schedules is expected, interim analyses will also combine the test schedules for comparison with the control for the primary endpoint.

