#### 17.3 Sample Size

#### **17.3.1. Main Trial**

The target sample size is 4000 patients, with numbers balanced equally in each randomised group. This provides 80% power (1-sided  $\alpha$  = 0.025 to allow for 1-sided hypothesis and multiple testing) to exclude an increase of 1.6% in the 5-year local relapse rate between each test group and the control, assuming a 5-year rate of 2% in the 40.05 Gy schedule (using START data and allowing for reduction in local relapse due to recent adoption of aromatase inhibitors and trastuzumab). As local relapse rates after radiotherapy are low, there is limited potential for reducing this even further when comparing different regimens in a trial. Therefore the aim is to test whether the local relapse rate in the test groups is at least as effective, and not more than 1.6% higher than in the control group. Since local relapse rates are so low, and no measurable difference in local relapse between the two test schedules is expected, interim analyses will also combine the test schedules for comparison with the control for the primary endpoint. This combined analysis will enable an excess of 1.3% in the 5-year local relapse rate of the test groups relative to the control to be excluded (80% power). As follow-up continues and more events accrue, the statistical power to compare each test schedule separately with the control will be higher. The calculations allow for up to 10% loss to follow-up / unevaluable.

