## Incomplete repair during a 24-hour inter-fraction interval

Turesson showed that a 24-hour inter-fraction interval is more sparing of late damage (telangiectasia) than a 4-hour interval. The difference was equivalent to 11% difference in fraction size [3]. Estimates of recovery half-time ( $T_{1/2}$ ) for late endpoints in humans are based on the CHART head and neck trial:  $T_{1/2}$  for telangiectasia was 3.8 hours and for fibrosis was 4.4 hours [4]. It is likely that repair beyond a 24-hours is very limited, and that no adjustment is needed to fraction size when moving from a 7-day to 1-day inter-fraction interval. The 2-year results of the FAST pilot study raised no concerns that an inter-fraction interval of 2 or 3 days leads to excessive late effects [2]. The EQD2.8Gy of the 5-fraction regimen delivered as one fraction per week in the FAST trial was estimated to be 54 Gy, but no marked change in breast appearance at 2 years was recorded in any of 30 patients treated with 30 Gy in 5 fractions over 15 days [2].. An element of incomplete repair at 24 hours (relative to 7 days) after 4 out of 5 test group fractions might lead to an estimated 1% increase in NTE, as illustrated for Test group 1 below if the second, third, fourth and fifth fractions follow on consecutive days and each deliver 5.5 Gy of absorbed dose instead of prescribed 5.4 Gy.

		*∆NTE			
Fractionation regimen	$EQD_{2.8Gy}(Gy)$	(%)			
5.4 Gy x 1	9.2	-			
5.5 Gy x 4	38.0	-			
5.4 Gy x 1 plus 5.5 Gy x 4	47.2	-10			
** 5.4 Gy x 5	46.1	-11			
* Estimated NTE rates relative to 50 Gy in 25 fractions  ** Test group 2, assuming 100% repair between fractions					

Despite a lack of evidence suggesting need for dose modification taking account of incomplete repair and/or a lower  $\alpha/\beta$  value for late NTE than that estimated in the START A and FAST trials, a second test dose level (26.0 Gy in 5 fractions of 5.2 Gy) is included, as applied in START A. This allows interpolation, if required, in order to identify a 5-fraction schedule iso-effective with 40.05 Gy in 15 fractions.

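### The primary comparison is defined at a 5-fraction dose level picked from the trial's late effects, while margin, alpha and power are set for each test group against control

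*Protocol*

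**What the plan says.** Section 17.2 gives two accounts of the main comparison.

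- The analysis is by allocated treatment in all randomised patients (intention to treat), and each test group is to be compared with the "Control group and treatment effects estimated separately".
- Having two test doses "allows minor adjustment, for example by interpolation, between test dose levels to identify the fraction size most closely resembling the control schedule", and the resemblance is to be judged "in terms of late change in breast/chest wall appearance and other adverse effects". The next sentence reads: "The primary comparison is the rate of local tumour control at this 5-fraction dose level compared to the 15-fraction control". The only thing that *this* can refer to is the level just identified from late effects.

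Appendix 2, in the part on incomplete repair, gives the reason for the second dose level: "This allows interpolation, if required, in order to identify a 5-fraction schedule iso-effective with 40.05 Gy in 15 fractions".

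Section 17.3.1 sizes the trial differently. On 4000 patients it says "This provides 80% power", and the stated purpose is "to exclude an increase of 1.6% in the 5-year local relapse rate between each test group and the control". The alpha used is given as "0.025 to allow for 1-sided hypothesis and multiple testing". Sections 7.2 and 10 allocate patients 1:1:1 to control, 27.0 Gy or 26.0 Gy, and to nothing between the two test doses.

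**The concern.** The sentence labelled primary names a comparison that differs from the one the design supports. Its dose level is chosen from the trial's own late-effect results. If it lies strictly between 26 and 27 Gy it is not an allocated treatment, so its relapse rate can only be modelled from the two arms and is not a direct intention-to-treat comparison. The protocol gives no margin, alpha or power for it.

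At stake is which result carries the non-inferiority claim. With two definitions in force, the choice between them could be made after the data are seen, and they need not lead to the same conclusion.

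**Working it through.** **1. The stated sample size is a pairwise one.** Inputs from 17.3.1: control 5-year relapse 2%, margin 1.6 points, one-sided alpha 0.025, power 80%, 10% loss; equal allocation to three groups.

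n per group = 2 × 0.02 × 0.98 × (1.960 + 0.842)² / 0.016² = 1202 evaluable. Then 1202 / 0.9 = 1336, and 3 × 1336 = 4008, against 4000 stated.

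With 4000 / 3 × 0.9 = 1200 evaluable per group, SE = √(2 × 0.0196 / 1200) = 0.00572, and power = Φ(0.016 / 0.00572 − 1.960) = 79.9%. With one-sided alpha of 0.05 or 0.0125 the total would be 3159 or 4854, so 4000 matches only one-sided 0.025 for each test group.

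**2. Where the identified dose would lie.** Appendix 2 uses α/β = 2.8 Gy for late effects, so EQD = D × (d + 2.8) / 4.8.

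- Control: 40.05 × 5.47 / 4.8 = 45.64 (printed 45.6)
- 27 Gy: 27 × 8.2 / 4.8 = 46.13 (printed 46.1)
- 26 Gy: 26 × 8.0 / 4.8 = 43.33 (printed 43.3)

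Weight on 27 Gy: w = (45.64 − 43.33) / (46.13 − 43.33) ≈ 0.83, which is about 26.8 Gy. The protocol's own model therefore expects a dose between the arms.

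**3. Can the definitions disagree?** Appendix 2 predicts relapse changes from 50 Gy of +2.4 (control), +3.6 (27 Gy) and +4.6 (26 Gy). Read as absolute points, the excess over control is:

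- 27 Gy: 3.6 − 2.4 = 1.2
- 26 Gy: 4.6 − 2.4 = 2.2
- interpolated: 0.83 × 1.2 + 0.17 × 2.2 ≈ 1.4

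The two arms fall on either side of 1.6, and the interpolated value falls below it. These are positions of assumed true differences, not forecasts of what the trial would show. Appendix 2 itself suggests that its predictions may be pessimistic.

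**4. Power at the interpolated dose.** For w × Test 1 + (1 − w) × Test 2 − Control, the variance is p(1 − p)/n × [1 + w² + (1 − w)²]. With p = 0.02, n = 1200, margin 1.6 points and w treated as known, power is 79.9% at w = 0 or 1, 85.6% at w = 0.83 and 89.8% at w = 0.5. Inside the tested range it is never below the pairwise figure. Extrapolation would lower it (56.2% at w = 1.5), but the protocol does not call for extrapolation.

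**5. Error with an estimated weight.** Simulation of 400,000 trials: 1200 per arm for relapse and 659 per arm for late effects (732 less 10%), w estimated from late effects and limited to 26–27 Gy, relapse independent of late effects. With both test arms at the margin, the one-sided error was about 0.025 for the interpolated contrast and about 0.027 for a single pairwise test. With all arms at 2%, power was 85–86% against 80%.

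**6. How often the match falls outside 26–27 Gy.** Assume a control late-effect rate of 35% and Appendix 2's late-effect differences as absolute points: 26 Gy, −18.8 + 12.3 = −6.5; 27 Gy, −11.1 + 12.3 = +1.2 as printed, or +1.4 as an alternative value. The share outside is 29–32% with 659 per arm and 23–26% with 1200. Reading the differences as relative instead gives 52% with 659 per arm.

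**7. Multiplicity of the pairwise design.** Two tests at one-sided 0.025 share a control group. The correlation is 0.36 with test arms at 3.6% and control at 2%, or 0.5 with equal variances. The chance of at least one false claim is 4.7% or 4.5% respectively.

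**The case against.** The strongest defence is that the pairwise analysis is already in the protocol. Section 17.2 compares each test group with control with confidence intervals, 17.3.1 gives the margin for each test group, and the multiplicity allowance there fits two comparisons. On this view only the label is in dispute. That largely stands, and it is why the repair is small. It does not remove the contradiction, because the label decides which result is tested against the margin.

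A reader might go further and infer any of the following. The document does not support them.

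- *The primary comparison must be at a dose nobody receives.* Interpolation is offered as an example in 17.2 and only if needed in Appendix 2, so the identified level could be one of the randomised arms. It would still be chosen from trial outcomes.
- *The comparison is undefined if the match lies outside 26–27 Gy.* The text speaks of adjusting between the test doses to find the closest one, which can be read as defaulting to the nearer arm.
- *The one-sided 0.025 is lost or the trial is underpowered.* Selection is on late effects, not relapse, and steps 4 and 5 show neither under their assumptions. Correlation between late effects and relapse, or relapse not linear in dose, could change this, but no such effect has been shown.

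Nor is this detail that can be left to an analysis plan. The protocol itself fixes the primary comparison, and does so in conflict with its own sample size.

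**Conclusion.** The contradiction is real and lies in the operative text. Section 17.2 names as primary a comparison at a dose level identified from late effects, about 26.8 Gy on Appendix 2's figures. The intention-to-treat comparison of allocated groups and all of 17.3.1 concern each test group against control. Only the pairwise comparison has a stated margin, alpha and power, and its 4000 is confirmed (4008; 79.9% power).

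The two definitions can point different ways: excesses of 1.2 and 2.2 for the arms and about 1.4 at the interpolated dose, against a margin of 1.6. This rests on reading Appendix 2's predictions as absolute points and is an illustration. The 23–32% chance of a match outside the tested range depends on assumed late-effect rates and is likewise only illustrative.

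The defect is an ambiguous, data-dependent primary comparison. It is not a demonstrated loss of error control or power.

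**What to change.** Replace the sentence on the primary comparison in 17.2 with wording to this effect: there are two primary comparisons, Test 1 v Control and Test 2 v Control, by intention to treat; each test group is non-inferior if the upper limit of the two-sided 95% confidence interval (one-sided 97.5%) for the difference in 5-year local relapse is below 1.6%.

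Add that one-sided 0.025 for each comparison gives a family-wise one-sided error of about 4.5–4.7%, in line with the multiplicity wording in 17.3.1. Label any relapse estimate at an interpolated iso-effective dose as secondary or exploratory.

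The cost is a wording amendment, made before the primary analysis. No patients, data or change in sample size are needed. The change takes no view on which dose is right.

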#### 17.3 Sample Size

#### **17.3.1. Main Trial**

The target sample size is 4000 patients, with numbers balanced equally in each randomised group. This provides 80% power (1-sided  $\alpha$  = 0.025 to allow for 1-sided hypothesis and multiple testing) to exclude an increase of 1.6% in the 5-year local relapse rate between each test group and the control, assuming a 5-year rate of 2% in the 40.05 Gy schedule (using START data and allowing for reduction in local relapse due to recent adoption of aromatase inhibitors and trastuzumab). As local relapse rates after radiotherapy are low, there is limited potential for reducing this even further when comparing different regimens in a trial. Therefore the aim is to test whether the local relapse rate in the test groups is at least as effective, and not more than 1.6% higher than in the control group. Since local relapse rates are so low, and no measurable difference in local relapse between the two test schedules is expected, interim analyses will also combine the test schedules for comparison with the control for the primary endpoint. This combined analysis will enable an excess of 1.3% in the 5-year local relapse rate of the test groups relative to the control to be excluded (80% power). As follow-up continues and more events accrue, the statistical power to compare each test schedule separately with the control will be higher. The calculations allow for up to 10% loss to follow-up / unevaluable.

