#### 7.2 Treatment allocation

Treatment allocation will be 1:1:1 and will use computer-generated random permuted blocks. Randomisation will be stratified by centre and risk group.

A fax will be sent to the randomising centre to confirm the trial number and treatment allocation.

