#### **APPENDIX 2: Selection of Test Dose Levels for FAST-Forward**

Assuming i) that the fractionation sensitivity of late normal tissue effects (NTE) is well-described by an  $\alpha/\beta$  value of 2.8, based on the results of the START A & FAST trials, ii) the slope of the dose response for NTE is well described by a  $\gamma$  value of 1.4, based on the START A trial and iii) complete repair of sublethal damage between daily fractions, the estimated equivalent total doses delivered in 2.0 Gy fractions assuming an  $\alpha/\beta$  value of 2.8 Gy (EQD2.8Gy) are shown below in a table that includes 50.0 Gy in 25 fractions as a reference schedule:

Fractionation regimen	$EQD_{2.8Gy}$ (Gy)	*ΔNTE (%)			
50 Gy/25Fr/5Wk (2.0 Gy/Fr)	50.0	reference			
40.05 Gy/15Fr/3Wk (2.67 Gy/Fr)	45.6	-12.3			
27 Gy/5Fr/1Wk (5.4 Gy/Fr)	46.1	-11.1			
26 Gy/5Fr/1Wk (5.2 Gy/Fr)	43.3	-18.8			
* Negative values indicate estimated NTE rates lower than after 50 Gy in 25 fractions					

Where tumour response is concerned, applying an  $\alpha/\beta$  value of 4.6 Gy generated by the START pilot and START A trials and  $\gamma$  = 0.2 based on START A, the estimated equivalent total doses delivered in 2.0 Gy fractions (EQD4.6Gy) are shown below in a table that includes 50 Gy in 25 fractions as a reference schedule:

Fractionation regimen	EQD 4.6Gy (Gy)	*∆Tumour Relapse (%)		
50 Gy/25Fr/5Wk (2.0 Gy/Fr)	50.0	reference		
40.05 Gy/15Fr/3Wk (2.67 Gy/Fr)	44.1	+2.4		
27 Gy/5Fr/1Wk (5.4 Gy/Fr)	41.0	+3.6		
26 Gy/5Fr/1Wk (5.2 Gy/Fr)	38.6	+4.6		
* Positive values indicate higher estimated levels of tumour relapse than after 50 Gy in 25 fractions				

Note that a 2.4% excess tumour relapse rate was excluded with >97% confidence in START B, where the HR for local relapse after 40.05 Gy in 15 fractions compared to 50.0 Gy in 25 fractions was 0.79 (95% CI=0.48-1.29). In other words, the local relapse rate was, if anything, slightly lower, not higher, after 15 compared to 25 fractions [1]. If treatment time explains part

or all of this effect, local relapse in the 1-week schedules will be lower than those estimated above.

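### The 1.3% excess quoted for the combined test-group analysis does not share the basis of the 1.6% per-group figure: at the stated alpha and 10% loss it is about 1.4%, and power is lower at early interim looks

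*Protocol*

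**What the plan says.** Section 17.3.1 sets the design: "The target sample size is 4000 patients, with numbers balanced equally in each randomised group". Section 7.2 adds: "Treatment allocation will be 1:1:1". The alpha is given as "0.025 to allow for 1-sided hypothesis and multiple testing", and the control rate by "assuming a 5-year rate of 2% in the 40.05 Gy schedule". On that basis each test group is to have 80% power to exclude an excess of 1.6%.

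The same section says that interim analyses will additionally pool the two test groups against control, and claims for the pooled comparison: "This combined analysis will enable an excess of 1.3% in the 5-year local relapse rate of the test groups" over control to be ruled out, with 80% power. It gives no separate alpha, event count or length of follow-up for this figure. It closes with a statement that covers both figures: "The calculations allow for up to 10% loss to follow-up / unevaluable".

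Section 17.4 makes the interim analyses yearly. Section 17.2 says that the calculations rest on survival methods with 5 years as the relevant time point. It justifies pooling on the ground that "no measurable difference in local relapse between the two test schedules is expected". Appendix 2 models excess tumour relapse of +3.6% for 27 Gy and +4.6% for 26 Gy, against 50 Gy in 25 fractions.

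**The concern.** Two power statements in one paragraph should rest on the same inputs unless the text says otherwise. Pooling two equal arms against one shrinks the standard error by a fixed factor, so the second figure can be checked against the first, and it comes out smaller than it should.

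What is at stake is how the data monitoring committee reads the pooled interim result. The protocol credits that comparison with slightly more precision than its stated inputs give. It also attaches a power figure that needs complete 5-year data to looks that may come well before then. Separately, the reason given for pooling sits uneasily with the protocol's own dose-response table.

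**Working it through.** **Inputs (sections 7.2 and 17.3.1).** N = 4000, allocated 1:1:1, so 1333 per group and 1333 v 2667 when pooled. With 10% loss: 1200 per group, 1200 v 2400 pooled. Control 5-year rate p = 0.02, so p(1−p) = 0.0196. 1-sided alpha 0.025 (z = 1.960), power 80% (z = 0.842), sum 2.802. True difference zero.

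**Formula.** Non-inferiority on a difference in proportions:
- SE = √[0.0196 × (1/n_c + 1/n_t)]
- excludable excess = 2.802 × SE
- power at excess m = Φ(m/SE − 1.960)

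**1. The per-group figure.**
- With 10% loss: SE = √[0.0196 × (2/1200)] = 0.00572; excess = 1.60%; power at 1.6% = 79.9%. This reproduces the plan.
- Without loss (1333 v 1333): excess = 1.52%.

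So the 1.6% figure is consistent with the stated 10% loss.

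**2. The pooled figure, same formula and alpha.**
- With 10% loss: SE = √[0.0196 × (1/1200 + 1/2400)] = 0.00495; excess = 1.39%; power at 1.3% = Φ(2.626 − 1.960) = 74.7%.
- Without loss: SE = √[0.0196 × (1/1333 + 1/2667)] = 0.00470; excess = 1.32%; power at 1.3% = 79.1%.

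A short check: pooling changes 1/n + 1/n into 1/n + 1/(2n), so the SE falls by √0.75 = 0.866, whatever the common rate, alpha or loss. 1.6% × 0.866 = 1.39%.

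**3. Other bases that might give 1.3%.**
- *1-sided alpha 0.05, 10% loss:* excess = (1.645 + 0.842) × 0.00495 = 1.23%; power at 1.3% = 83.7%. The figure would then read 1.2%, and the protocol does not state this alpha.
- *Log-hazard scale.* A 1.6% excess is a hazard ratio of ln 0.964 / ln 0.98 = 1.815; a 1.3% excess is ln 0.967 / ln 0.98 = 1.661. Power = Φ(ln HR × √[D × w] − 1.960), with D events and w = 1/4 for a pair or 2/9 for the pooled 1:2 split. At 5 years with equal rates, D = 2400 × 0.02 = 48 per pair and 72 pooled, giving 54% power at 1.6% and 53% at 1.3%. Neither stated figure is reached. If instead events accrue until 1.6% just has 80% power, 2.802² / (0.25 × 0.596²) ≈ 88 per pair, or 133 in three arms. The pooled excess is then 1.33%, with 78.7% power at 1.3%. At a hazard of −ln 0.98 / 5 = 0.00404 per year, 88 events in 2400 patients need about 9 years' mean follow-up.

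**4. Interim looks.** With a fraction f of the 5-year information, power at 1.3% = Φ(2.626 × √f − 1.960), at alpha 0.025 and 10% loss:

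| f | 0.25 | 0.50 | 0.75 | 0.90 | 1.00 |
|---|---|---|---|---|---|
| Power | 25.9% | 45.9% | 62.3% | 70.3% | 74.7% |

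The fractions are illustrative; the protocol does not tie its looks to amounts of information.

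**5. The pooling premise.** Appendix 2's tabled values differ by 4.6 − 3.6 = 1.0 point, which is 1.0/1.6 = 63% of the per-group margin. Power to detect 2% v 3% with 1200 per arm (2-sided 0.05) is about 35%.

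**The case against.** The strongest reply is that the protocol fixes neither an alpha nor a formula for the pooled comparison. Part of the 0.025 is explained by multiple testing, so a single pooled test might use more, and section 17.2 names survival methods. This stands to the extent that a reader should not infer that 1.3% is unattainable on any basis. At 1-sided 0.05 power exceeds 80%, and the long-follow-up log-hazard route rounds to 1.3%. But the first uses an alpha that the document does not state, and the second needs follow-up far longer than a figure attached to interim analyses suggests.

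Rounding gives a further route. At a loss of about 4.5% the two excesses are 1.519/√0.955 = 1.554% and 1.316/√0.955 = 1.347%, which round to 1.6% and 1.3%. The stated allowance, however, is up to 10%.

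It is also fair to say that low power at early looks is a general fact, and that late yearly looks can have complete 5-year data. A reader might infer that every interim analysis falls short of the final figure; the 10-year follow-up does not support that. What stands is that the text gives 80% power with no follow-up condition.

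On the premise, a reader might infer that Appendix 2 contradicts it. It does not. The claim is about a *measurable* difference, and 1.0 point would usually go undetected. The table's footnote, "Positive values indicate higher estimated levels of tumour relapse than after 50 Gy in 25 fractions", makes plain that the comparison is with 50 Gy rather than between test schedules. The appendix also qualifies its own model: it reports the 2.4% excess modelled for the control schedule as excluded by an earlier randomised trial, and it allows that a treatment-time effect would lower relapse in the 1-week schedules.

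Nor does pooling leave a one-arm excess unexamined, because section 17.2 compares each test group with control separately and the pooled analysis is additional.

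**Conclusion.** The point holds as a correction to one stated figure. On the inputs that section 17.3.1 gives (2% control rate, 1-sided alpha 0.025, 10% loss) and the formula that reproduces its 1.6%, the pooled analysis excludes about 1.4% with 80% power, or has about 75% power at 1.3%. The discrepancy is 0.09 of a percentage point, or about 5 points of power. It rests on the alpha and loss carrying over to the pooled comparison and on complete 5-year data. Before those data are complete, power is lower still, for example about 46% at half the information.

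The pooling premise is in tension with the 1.0-point gap modelled in Appendix 2, and the two places need reconciling; that is secondary. The primary per-group comparison and the sample size of 4000 are unaffected.

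**What to change.** In section 17.3.1, do one of two things:
- restate the pooled figure as an excess of about 1.4% (80% power, 1-sided alpha 0.025, 10% loss) once 5-year follow-up is complete, and add that power is lower at earlier interim analyses; or
- keep 1.3% and state the different alpha, or the events and follow-up, on which it rests.

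In sections 17.2 and 17.3.1, reconcile the expectation about the two test schedules with Appendix 2. One sentence would do, for instance that a difference of the modelled size is unlikely to be detectable in this trial and that the appendix's caveats apply.

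The cost is one figure and two or three sentences. The stated excess becomes slightly less favourable. No change to recruitment is called for: holding 1.3% at 80% power with 10% loss would need 1366 evaluable controls, so 3 × 1366 = 4098 evaluable in total and 4098/0.9, about 4554, randomised. That is out of proportion for a supplementary interim comparison.
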